TLF	Table Number	Title	Analysis Set	Unique (U)/ Repeat (R)	Section	Efficacy/ Safety/ Standard	Topline	IA
Table	14.3.4.2.3.1	Summary of Clinically Notable Laboratory Results by Visit - Chemistry (Liver)	Open-label losmapimod (Pre-COVID-19) Analysis Set	R	9.2.2	Safety		
Table	14.3.4.3	Change from Baseline in Coagulation	Safety Analysis Set	R	9.2.3	Safety		
Table	14.3.4.3.1	Change from Baseline in Coagulation	Open-label losmapimod (Pre-COVID-19) Analysis Set	R	9.2.3	Safety		
Table	14.3.4.4	Change from Baseline in Urinalysis	Safety Analysis Set	R	9.2.3	Safety		
Table	14.3.4.4.1	Change from Baseline in Urinalysis	Open-label losmapimod (Pre-COVID-19) Analysis Set	R	9.2.3	Safety		
Table	14.3.5.1	Change from Baseline in Vital Signs by Visit	Safety Analysis Set	U	9.3	Safety		
Table	14.3.5.1.1	Change from Baseline in Vital Signs by Visit	Open-label losmapimod (Pre-COVID-19) Analysis Set	R	9.3	Safety		
Table	14.3.5.2.1	Physical Examination	Safety Analysis Set	U	9.4	Safety		
Table	14.3.5.2.1.1	Physical Examination	Open-label losmapimod (Pre-COVID-19) Analysis Set	R	9.4	Safety		
Table	14.3.5.2.2	Neurological Examination Results	Safety Analysis Set	U	9.4	Safety		
Table	14.3.5.2.2.1	Neurological Examination Results	Open-label losmapimod (Pre-COVID-19) Analysis Set	R	9.4	Safety		
Table	14.3.5.3.1	Change from Baseline in Electrocardiogram Results	Safety Analysis Set	U	9.5	Safety		
Table	14.3.5.3.1.1	Change from Baseline in Electrocardiogram Results	Open-label losmapimod (Pre-COVID-19) Analysis Set	R	9.5	Safety		

TLF	Table Number	Title	Analysis Set	Unique (U)/Repeat (R)	Section	Efficacy/Safety/Standard	Topline	IA
Table	14.3.5.3.2	Electrocardiogram Interpretation by Visit	Safety Analysis Set	U	9.5	Safety		
Table	14.3.5.3.2.1	Electrocardiogram Interpretation by Visit	Open-label losmapimod (Pre-COVID-19) Analysis Set	R	9.5	Safety		
Table	14.3.5.3.3	Summary of QTc Values	Safety Analysis Set	U	9.5	Safety		
Table	14.3.5.3.3.1	Summary of QTc Values	Open-label losmapimod (Pre-COVID-19) Analysis Set	R	9.5	Safety		

15.9. List of Planned Data Listings

TLF	Table Number	Title	Analysis Set	Unique (U)/Repeat (R)	Section	Efficacy/Safety/Standard	Topline	IA
Listing	16.2.1	Subject Disposition	All Screened Subjects	U	5.1	Standard		
Listing	16.2.2	Protocol Deviations	FAS	U	5.2	Standard		
Listing	16.2.3	Analysis Set	All Screened Subjects	U	5.1	Standard		
Listing	16.2.4.1	Demographics and Baseline Disease Characteristics	FAS	U	6.1	Standard		
Listing	16.2.4.3	Medical History	FAS	U	6.3	Standard		
Listing	16.2.4.4	Prior and Concomitant Medications	Safety Analysis Set	U	7.1.1 and 7.1.2	Standard		
Listing	16.2.4.5	Physical Examination	Safety Analysis Set	U	9.4	Safety		
Listing	16.2.4.6	Neurological Examination Result	Safety Analysis Set	U	9.4	Safety		
Listing	16.2.5.1	Study Drug Accountability	Safety Analysis Set	U	7.2.1	Standard		
Listing	16.2.5.2	Study Drug Administration	Safety Analysis Set	U	7.2.2	Standard		
Listing	16.2.5.3.1	Individual Losmapimod Concentration	PK Analysis Set	U	10	Efficacy		

TLF	Table Number	Title	Analysis Set	Unique (U)/Repeat (R)	Section	Efficacy/Safety/Standard	Topline	IA
Listing	16.2.5.3.2	Target Engagement Estimates	PD Analysis Set	U	10	Efficacy		
Listing	16.2.6.1.1	DUX4 Activity (Normalized Delta CT Value)	FAS	U	8.1	Efficacy		
Listing	16.2.6.1.2	DUX4 Score	FAS	U	8.1	Efficacy		
Listing	16.3.6.2	Fat Fraction, Lean Muscle Tissue Volume, and Muscle Fat Infiltration	FAS	U	8.2	Efficacy		
Listing	16.3.6.3.1.1	Reachable Work Space	FAS	U	8.3.1	Efficacy		
Listing	16.3.6.3.1.2	Functional Work Space	FAS	U	8.3.1	Efficacy		
Listing	16.3.6.3.2.1	Classic Timed Up and Go (TUG)	FAS	U	8.3.2	Efficacy		
Listing	16.3.6.3.2.2	Optimized Timed Up and Go (TUG)	FAS	U	8.3.2	Efficacy		
Listing	16.3.6.3.3	Muscle Strength by Handheld Quantitative Dynamometry	FAS	U	8.3.3	Efficacy		
Listing	16.3.6.3.4	Motor Function Measure (MFM) Domain 1	FAS	U	8.3.4	Efficacy		
Listing	16.3.6.3.5	Facioscapulohumeral Muscular Dystrophy Health Index (FSHD-HI)	FAS	U	8.3.5	Efficacy		
Listing	16.3.6.3.6	Patient Global Impression of Change (PGIC)	FAS	U	8.3.6	Efficacy		
Listing	16.2.7.1	Adverse Events	Safety Analysis Set	U	9.1	Safety		
Listing	16.2.7.2	Serious Adverse Events	Safety Analysis Set	R	9.1	Safety		
Listing	16.2.7.3	Adverse Events Leading to Treatment Discontinuation	Safety Analysis Set	R	9.1	Safety		
Listing	16.2.7.4	Adverse Events Leading to Study Withdrawal	Safety Analysis Set	R	9.1	Safety		
Listing	16.2.7.5	Deaths	Safety Analysis Set	R	9.1	Safety		
Listing	16.2.8.1	Laboratory Results – Hematology	Safety Analysis Set	U	9.2.1	Safety		
Listing	16.2.8.2.1	Laboratory Results – Chemistry	Safety Analysis Set	R	9.2.2	Safety		
Listing	16.2.8.2.2	Laboratory Results of Subjects with Incidence of ALT/AST $\geq 3 \times$ ULN and Total Bilirubin $\geq 2 \times$ ULN and ALP $< 2 \times$ ULN	Safety Analysis Set	R	9.2.2	Safety		
Listing	16.2.8.3	Laboratory Results – Urinalysis	Safety Analysis Set	R	9.2.3	Safety		
Listing	16.2.8.4	Laboratory Results – Coagulation	Safety Analysis Set	R	9.2.4	Safety		
Listing	16.2.8.5	Vital Sign Results	Safety Analysis Set	U	9.3	Safety		
Listing	16.2.8.6	Electrocardiogram Results	Safety Analysis Set	U	9.5	Safety		

5.4. REACHABLE WORK SPACE WITH AND WITHOUT WEIGHTS.....	4
5.5. FSHD TUG	4
5.6. PGIC.....	5
 	
6. PHARMACODYNAMICS ANALYSIS	5
REFERENCES.....	5

1. Introduction

The purpose of this addendum to the final statistical analysis plan (SAP), dated 28May2020, is to describe the additional analyses that will be performed as well as to provide details on the analyses that will no longer be performed. In addition, this document will also correct some typos in both SAP and protocol.

2. Analysis Set

2.1. Pharmacodynamics Analysis Set

The Pharmacodynamic Analysis Set definition is updated to:

The PD Analysis Set will consist of all subjects who receive at least 1 dose of study drug and have evaluable PD data.

2.2. Per Protocol Analysis Set

The following are considered as significant protocol deviations in the study that may have a substantial impact on the primary endpoint. Thus, subjects in Full Analysis Set who satisfy any of the following criteria will be excluded from the Per Protocol Analysis Set.

- 1) Study drug compliance of below 80% before the post-baseline muscle biopsy assessment, which is either on Week 16 or Week 36.
- 2) Certain major protocol deviation identified from the protocol deviation tracker before database lock.
- 3) Certain prohibited medications.
- 4) Violation of inclusion/exclusion criteria.

3. General Statistical Considerations

3.1. Reporting Conventions

Presentation of continuous and quantitative variables will also include standard errors (SE).

3.2. Subgroup

For the subgroup analysis, RWS will be presented according to protocol type instead of just presenting subjects who have above shoulder movements.

1. Protocol Type (High or Low - for Subjects Who Completed RWS Protocol With Above Shoulder Movements or Below Shoulder Movements at Baseline).
2. Protocol Type (High or Low - for Subjects Who Completed RWS Protocol With Above Shoulder Movements or Below Shoulder Movements All Through the Study).

Subgroup no. 8, subjects completing the classical TUG, without an assisted device at baseline, will be updated to also consider subjects with assisted device at baseline. Hence, the subgroup presentation will be based according to use or non-use of assisted device at baseline for subjects who completed the classical TUG.

In the same manner, subgroup no. 9, subjects completing the FSHD TUG, without an assisted device, at baseline, will be updated to consider subjects with assisted device at baseline. Hence, the subgroup presentation will be based according to use or non-use of assisted device at baseline for subjects who completed the FSHD TUG.

Subgroup no. 10, MFF_{tot}, LMV_{tot} and MFI_{tot} with thresholds at the median of observed baseline data, will be based on the Longitudinal Reference Value at Screening.

4. Treatment Compliance

Additional categories for compliance will be included and the existing categories will be updated as follows:

- <40%
- 40-<60%
- 60-<80%
- 80-<120%
- >120%

5. Efficacy Analysis

5.1. Mixed Effects Model for Repeated Measures

The Kenward-Roger approximation will be used to estimate denominator degrees of freedom.

5.2. Change from Baseline in DUX4 Activity in Skeletal Muscle at Week 16 or Week 36

Fold change will be presented in Table 14.2.2.1.1 (Change from Baseline in DUX4 Activity (DUX4 Score 1) Full Analysis Set, Table 14.2.2.1.2 (Change from Baseline in DUX4 Activity (DUX4 Score 1) by Baseline Repeat Category Full Analysis Set), Table 14.2.2.1.6 (Change from Baseline in DUX4 Activity (DUX4 Score 1) by Baseline DUX4 Score 1 Full Analysis Set), and Table 14.2.2.2.5.1 (Sensitivity Analysis: Change from Baseline in DUX4 Activity (DUX4 Score 1) by Timepoint Full Analysis Set). Fold change is the difference in the natural log (ln) transformed values of DUX 4 Score 1 at Week 36 or Week 16 DUX4 Score 1 and Baseline; then using the exponential function to return the computation to the original scale. The summary of fold change will include n, mean, SD, SE, median, minimum, maximum, and geometric mean. Geometric mean is derived as the arithmetic mean of the ln-transformed values of fold change of DUX4 Score 1; then using the exponential function to return the computation to the original scale. For the repeat category subgroup analysis, the repeat category will be excluded as fixed effect from the model.

In addition, an ANCOVA model will be used to analyze the change from baseline in the ln-transformed value of DUX4 Score 1, with repeat number category and treatment group as fixed effects and ln-transformed baseline DUX4 Score 1 in affected skeletal muscle as a covariate. Then, the point estimates which include within-group least-squares (LS) means and 2-sided 95% CIs will be back transformed using the exponential function to return the values to the original scale as the ratio of means and the associated 2-sided 95% CIs.

An additional sensitivity analysis will be done using the highest two expression transcripts. The DUX4 Score 1 of highest two expression transcript is derived as the mean of 2 genes or more (if there is a tie in values) with the highest expressing values at baseline. Similar methods in Section 8.2 of the SAP will be used to analyze the change from baseline in the DUX4 activity of highest two expression transcripts

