8.1. Hypothesis Testing Procedure for Key Study Endpoints

A fixed sequential testing procedure will be used to control for the experiment-wise Type I Error to test the following key study endpoints as ordered below:

- DUX4 change from baseline at Week 16 or Week 36 [DUX4 Score 1. See [Section 8.2](#)]
- LMV change from baseline at Week 48 [Total LMV, composite of assessments from multiple muscles. See [Section 8.3](#)]

- FSHD TUG change from baseline at Week 48 [average completion time of FSHD TUG. See [Section 8.4.2](#)]

At each step in this sequential ordering, statistical significance for the endpoint will be claimed only if the p-value for the test is less than the final alpha obtained from the O'Brien-Fleming Spending Function ([Table 12-1](#)) and the p-values for the tests for all previous endpoints in the list are also less than the final alpha provided.

The testing hierarchy will be as follows:

- If the p-value for the test of the comparison of DUX4 change from baseline between the two treatment groups is less than the final alpha, then the comparison of the LMV change from baseline will be conducted. If the p-value from this comparison is also less than the final alpha, then the comparison of the FSHD TUG change from baseline will be conducted.
- Once a p-value is greater than or equal to the final alpha for the current endpoint being evaluated, then only the tests for the preceding endpoints will be considered significant.
- The formal statistical tests for any of the endpoints will be considered statistically nonsignificant when the test has a p-value of greater than or equal to final alpha. However, nominal p-values will still be provided for these endpoints.

8.2. Change from Baseline in DUX4 Activity in Skeletal Muscle at Week 16 or Week 36

A subset of DUX4-gene transcripts will be measured in skeletal muscle biopsies, using a validated QRT-PCR assay, to assess the treatment effect of losmapimod over placebo on aberrant DUX4 activity. A mean DUX4 score (DUX4 Score 1) will be derived for each patient, at each time point based on normalized gene expression values for the panel of pre-selected genes. DUX4 Score 1 is a mean of normalized (delta-CT) for the pre-selected panel of 6 genes, by subject, for each timepoint.

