15.1. The Steps from Raw QPCR Ct to Statistical Analysis

1. Raw Cts from qPCR are determined for DUX4 regulated genes using a validated assay (Fluidigm), described in [Appendix 15.2](#).
2. The raw Cts from the genes are normalized to reference (housekeeping) genes using the process described in [Appendix 15.3](#). The document also describes the method for selecting the reference genes.
3. A mean DUX4 score is created for each subject using the normalized data, at baseline and post-baseline, using the derivation described in [Appendix 15.4](#).
 - a. Six DUX4-regulated gene transcripts were selected, a priori, to be in a mean DUX4 score. The process of selection of these 6 genes is detailed in [Appendix 15.5](#).
4. An ANCOVA regression model is then used to test the hypothesis for change in the composite score between treatment arms.

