15.4. Derivation of DUX4 Score from Delta CT

Select only rows pertaining to the following 6 gene transcripts: CCNA1; KHDC1L; MBD3L2; PRAMEF6; SLC34A2; ZSCAN4

DUX4 Score 1: Mean

Take the mean of delta-CT values across all 6 transcripts, by subject, by timepoint

DUX4 Score 2: Standardized Z-Score Composite

Step 1 (Pre-Treatment data only): (By gene transcript)

- I. Calculate Mean (measure of average) of delta CT
- II. Calculate standard deviation (measure of variability) of delta CT

Step 2 (Pre-treatment and post-treatment: By gene transcript; by subject)

- I. Use variability obtained in Step 1 to calculate standardized score per gene transcript, per patient:

$$\begin{aligned} \text{Standardized Score} \\ = (\text{Normalized Delta Ct Value} - \text{Mean}) \div \text{Standard Deviation} \end{aligned}$$

- a. **Rationale:** Standardize all gene measures to the same scale; reduce the impact of highly variable genes in the final composite measure
- II. Calculate mean of standardized scores for each patient, across all genes, by visit.
 - a. Each patient's final score is the mean standardized score across multiple transcripts.
 - b. This "composite score" is then used in the analysis for change from baseline.

DUX4 Score 3: Median

Take the median of delta-CT values across all 6 transcripts, by subject, by timepoint

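### The addendum's DUX4 fold change divides one log-scale score by another, so it is not an expression fold change unless the unseen assay appendices convert the score to a linear scale

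*SAP*

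**What the plan says.** SAP Section 8.2 defines the primary variable: "DUX4 Score 1 is a mean of normalized (delta-CT) for the pre-selected panel of 6 genes, by subject, for each timepoint". Appendix 15.4, headed "Derivation of DUX4 Score from Delta CT", gives the same rule: "Take the mean of delta-CT values across all 6 transcripts, by subject, by timepoint". Appendix 15.1 describes the step before it: "The raw Cts from the genes are normalized to reference (housekeeping) genes using the process described in" Appendix 15.3. The planned listing of the normalized data (SAP Section 15.9, Listing 16.2.6.1.1) is titled "DUX4 Activity (Normalized Delta CT Value").

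Addendum Section 5.2 then adds two outputs.

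- **Fold change per subject.** "Fold change is the difference in the natural log (ln) transformed values of DUX 4 Score 1 at Week 36 or Week 16" and baseline, followed by exponentiation. The assignment starts with "Fold change will be presented in Table 14.2.2.1.1" and goes on to Tables 14.2.2.1.2, 14.2.2.1.6 and 14.2.2.2.5.1. The summary includes a geometric mean.
- **An extra ANCOVA on ln(Score 1).** In this model "the point estimates which include within-group least-squares (LS) means and 2-sided 95% CIs will be back transformed using the exponential function" and presented as a ratio of means. The section names no table for it and no between-arm contrast.

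The primary ANCOVA in SAP Section 8.2 stays on the untransformed change in Score 1.

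**The concern.** Delta-CT is a number of amplification cycles, so it already lies on a log scale. An expression fold change comes from exponentiating a difference of two delta-CT values. The addendum takes logs of the scores a second time and ends with one log-scale value divided by another. Such a ratio has no fixed relation to the change in expression: the same biological effect gives different values at different baselines, or with different reference genes. The formula also fails for any score at or below zero.

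The same recipe is sound in SAP Section 11, because there the input is a pHSP27 concentration, which is linear.

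What is at stake is how the effect size is read. The figure is printed in the primary-endpoint table, and Protocol Section 3.2.1 predicts a reduction of more than 50% in DUX4-dependent targets. A reader would naturally compare the two.

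**Working it through.** The documents state no fold-change figure, so there is none to reproduce.

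**Step 1: what the formula computes.** exp[ln(post) − ln(base)] = post / base.

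**Step 2: the scale of the input.** SAP Section 8.2, Appendix 15.4 (heading and rule) and Listing 16.2.6.1.1 all call the input delta-CT. No visible step converts it to linear expression. A sign flip or an added constant in Appendix 15.3 would leave it on a log scale; only exponentiation would make post / base an expression ratio. For example, if the scores were linear (2^5 falling to 2^4), the formula would correctly give 16/32 = 0.50.

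**Step 3: the sign.** It is not stated. The worst-case imputation in SAP Section 8.2.1 fills missing post-baseline values with the highest score, and Addendum Section 5.2 speaks of the transcripts with the highest expression values. Both suggest that a higher score means more expression, and that reading is used below.

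**Step 4: illustration.** All baselines are assumptions. A true halving at base 2 is a fall of one cycle, so the true fold change is 2^(−1) = 0.50. The addendum formula gives (b − 1)/b:

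| Baseline b | Addendum value | Truth |
|---|---|---|
| 1.2 | 0.2/1.2 = 0.17 | 0.50 |
| 1.5 | 0.5/1.5 = 0.33 | 0.50 |
| 2 | 1/2 = 0.50 | 0.50 |
| 5 | 4/5 = 0.80 | 0.50 |
| 10 | 9/10 = 0.90 | 0.50 |
| 12 | 11/12 = 0.92 | 0.50 |

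Under the opposite sign the halving is a rise of one cycle. The formula then reads 1.50 at baseline 2, 1.20 at 5 and 1.08 at 12, which is the wrong direction.

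**Step 5: the zero point.** Suppose other reference genes shift all scores by a constant. A one-cycle fall from baseline 5 then reads:

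- shift −2: 2/3 = 0.67
- no shift: 4/5 = 0.80
- shift +2: 6/7 = 0.86
- shift +5: 9/10 = 0.90

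**Step 6: Table 14.2.2.1.6.** This table uses the nested baseline thresholds of SAP Section 4.6 (at or above Q1, Q2, Q3). Simulating a uniform halving gives geometric means of 0.81, 0.83 and 0.84 at baseline mean 5 (SD 1), and 0.91, 0.91 and 0.92 at mean 10 (SD 2). The spurious gradient is small, but the level is wrong throughout.

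**Step 7: the ln-ANCOVA.** The simulated model had treatment, a repeat-category factor and ln baseline, with a one-cycle fall on drug and no change on placebo. In the noisy case the SD of change was 1/0.70 = 1.43 cycles, which assumes that one cycle is the planned effect size of 0.70 (SAP Section 4.7). Scores at or below zero were dropped.

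| Case | Drug (truth 0.50) | Placebo (truth 1.00) |
|---|---|---|
| Mean 5, no noise | 0.79 | 1.00 |
| Mean 10, no noise | 0.90 | 1.00 |
| Mean 5, SD of change 1.43 | 0.73 | 0.95 |
| Mean 10, SD of change 1.43 | 0.88 | 0.99 |

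Raising 2 to the LS means of the untransformed ANCOVA returns 0.50 and 1.00 in every case. This is expected, because the data were generated as a one-cycle shift at base 2.

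**Step 8: undefined values.** With that SD and baseline mean 5, 1.09% of drug-arm post-baseline scores are at or below zero. Among 34 subjects the chance of at least one is 1 − (1 − 0.0109)^34 = 0.31. At mean 10 the rate is about 0.01%, and the chance is 0.004.

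**Step 9: the amplification base.** One cycle corresponds to 1/1.8 = 0.556, 1/1.9 = 0.526 or 1/2.0 = 0.500, so the base has to be stated.

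**The case against.** The strongest objection is that the deciding text lies in Appendices 15.2 and 15.3, which were not available. Plain delta-CT, target minus reference, falls as expression rises, yet the SAP treats a high score as worse. So some step may have changed the score, and that step could be 2^(−delta-CT), which would make the addendum correct. Use of ln and the wish to return to an original scale fit an author who believed the score to be positive and linear. A heading and a listing title are labels, not definitions.

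This stands as a condition but does not overturn the point. A sign flip explains the direction equally well and leaves the score on a log scale. The description as delta-CT is also not confined to labels: it is in the operative rules of Section 8.2 and Appendix 15.4.

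The objection on size also stands in part. Without delta-CT values even the direction of the error is unknown: the formula understates the effect above baseline 2, is exact at 2, and overstates it below 2. The noisy runs rest on several stacked assumptions. The comparison with the protocol's 50% prediction is an inference about readers, since no section sets a fold-change criterion. Finally, one amplification base for six transcripts is itself an assumption that the assay appendices would have to support.

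**Conclusion.** The point holds on the visible text. Addendum Section 5.2 defines post-score divided by baseline score, and with Score 1 as a mean of delta-CT this is not an expression fold change. The back-transformed ln-ANCOVA has the same fault. The conclusion is conditional on Appendices 15.2 and 15.3 not converting to linear expression.

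The size cannot be fixed from the documents. Over assumed baselines of 5 to 10 a true halving would print as a 10% to 20% fall; below 2 the effect would be exaggerated. Whether non-positive scores occur is unknown.

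The primary ANCOVA works on differences of the untransformed score, so its p-value, the alpha and the testing hierarchy are untouched. The harm is a misstated effect size printed beside the primary result. It should be corrected.

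**What to change.** 1. State in the addendum the sign of delta-CT and the amplification base, taken from the assay appendices.
2. Define each subject's fold change as that base raised to the signed change in Score 1, so that values above 1 mean more expression. Keep the planned descriptive statistics, including the geometric mean.
3. Drop the ANCOVA on ln(Score 1). Apply the transform in item 2 to the LS means, their difference and the confidence limits from the primary ANCOVA of SAP Section 8.2.
4. If Appendix 15.3 does convert to linear expression, say so in Section 8.2 and Appendix 15.4 and stop calling the input delta-CT. The addendum formula can then stand.

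The cost is addendum wording, the fold-change rows of four tables and the ln-ANCOVA output. No new data or model is needed, and the primary analysis stays as it is.

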5.3. MSK MRI Muscle Fat Fraction, Lean Muscle Volume and Muscle Fat Infiltration

The cross-sectional composite scores will be used to correlate the results with Clinical Outcome Assessments (i.e. TUG and RWS). Only summary statistics will be presented for these parameters.

The cross-sectional results will be further presented by extremity i.e. upper extremity, lower extremity, and total results. The convention that will be used to get extremity equivalent of the cross-sectional results is provided in Table 5-3.

Table 5-3. Extremity Equivalent of MRI Cross-sectional Results.

MRI Cross-sectional Results	Equivalent Extremity
FSHD TUG Cross-sectional	Lower extremity (LE)
RWS Right Cross-sectional	Right upper extremity (RUE)
RWS Left Cross-sectional	Left upper extremity (LUE)
RUE + LUE	Upper extremity (UE)
LE + RUE + LUE	Total

In addition, Spearman correlation coefficients will be used to assess relationships between the by extremity MRI results and classical and FSHD TUG and RWS results by visit. The Spearman correlation coefficient and p-value will be calculated within each treatment and presented in a table. This will also be graphically presented using scatterplots. Specifically, the following relationships will be assessed:

- LE vs. FSHD-TUG
- LE vs. Classical TUG
- RUE vs. RWS
- LUE vs. RWS
- UE vs. RWS

- TOTAL vs. FSHD-TUG
- TOTAL vs. Classical TUG
- TOTAL vs. RWS

The longitudinal composite scores are used to measure the change from baseline at each post-baseline visit. This is the result that will be used in the MMRM model.

